6.3. Missing data

If outcome data are missing for >15% of participants we will report results from sensitivity analyses for missing data [4,5]. We selected 15% missing because trials with >20% missing values are thought to be a concern for bias [6]. The primary analysis will assume outcomes are

missing completely at random. We will relax this assumption slightly, assuming that outcomes are missing at random (MAR) with an inverse-probability weighted (IPW) estimator. We will model the probability of censoring as a function of baseline patient characteristics with a logistic regression model, and will use the inverse of the predicted probabilities from the model to re-weight the analysis population to reflect the full study population at the time of enrollment, using a doubly-robust targeted maximum likelihood estimator that also includes an outcome model using the same covariates [7]. Baseline characteristics used in the censoring model will include treatment arm, site, age, sex, occupation, medication use at enrollment, eye trauma, ocular measures at enrollment (infiltrate and/or scar size, depth, epithelial defect size, duration of symptoms, BSCVA). We will additionally consider a range of scenarios assuming the outcomes are missing not at random (MNAR), *i.e.* systematically, using a pattern mixture model approach described by Little et al. [4], whereby we model BSCVA with a linear model as a function of covariates listed for the IPW estimator; missing outcomes will then be imputed using the model fit to predict, adding a shift parameter, Δ , that we vary across a range of values.

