### 9.3 POPULATIONS FOR ANALYSES

Our analysis will adhere strictly to the intent-to-treat principle. All participants randomized will be analyzed according to their allocation.

**Missing Outcomes:** We distinguish two kinds of missing data: missing data in covariates, and missing data for outcomes. For the latter, we distinguish simple loss to follow-up (as when a patient has needed to move out of the area) from data missing because of the occurrence of a medical event (such as the loss of an eye). We will always report the results of complete case analysis, although such results are known to be biased. In the event of missing baseline covariates among >10% of patients, we will use regression based multiple imputation (with at least 100 replicates) to impute these missing covariates (based only on other variables available at baseline). To compare with the complete case analysis, we will also report multiple-imputation based analysis for missing outcomes (or equivalently, likelihood methods which integrate over the missing outcome data based on the same assumption of missingness at random); such analyses are important to report because of the intent to treat principle. Finally, we conduct sensitivity analyses in which the data are not assumed missing at random, to assess how extreme the missing values would need to be to change the conclusions of the study. We propose use of the R package mice (Multiple Imputation by Chained Equations) for multiple imputation; other choices are available and would serve equally well.

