3.3. Sample size

The trial's sample size calculation was based on the primary outcome, 6-month BSCVA. We informed the calculation with measurements from the first Steroids for Corneal Ulcers Trial (SCUT), among patients enrolled with between 20/60 and 20/400 vision. The SCUT trial measured BSCVA at baseline, 3-months, and 12-months. We conservatively used the 12-month outcome measure for the calculations since there was no 6-month measurement. The standard deviation of BSCVA at 12 months was 0.293. Since the primary analysis will adjust for baseline BSCVA, we used an estimate of the residual standard deviation, which is $SD_r = SD\sqrt{1 - r^2}$, where r is the correlation between the baseline measure and primary endpoint. In SCUT, the correlation between baseline and 12-month BSCVA among patients with between 20/60 and 20/400 vision at enrollment was 0.216. We thus assumed a residual standard deviation of $0.293\sqrt{1 - 0.216^2} = 0.286$.

Assuming a significance level of 0.05, allowing for approximately 15% loss to follow up, we estimate that we will have 90% power to detect a 1.1-line difference (logMAR 0.11) between groups with 165 study participants per arm (330 total). For the same sample size and under the same assumptions, the detectable difference at 80% power is 1.0-lines (logMAR 0.10). These calculations were based on the standard power formula for the T-test (using an estimated residual standard deviation).

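### SAP 6.3 requires its missing-outcome sensitivity analyses only above 15% missing, about the planned loss, although Protocol 9.3 promises them at any level of loss

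*SAP*

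**What the plan says.** SAP 6.3 opens with a condition: "If outcome data are missing for >15% of participants we will report results from sensitivity analyses for missing data". It gives the reason next: "We selected 15% missing because trials with >20% missing values are thought to be a concern for bias". The primary analysis assumes outcomes are missing completely at random. Two further analyses follow. One relaxes the assumption, "assuming that outcomes are missing at random (MAR) with an inverse-probability weighted (IPW) estimator", carried out as a doubly robust targeted maximum likelihood estimator. The other is a pattern-mixture MNAR analysis in which "missing outcomes will then be imputed using the model fit to predict, adding a shift parameter" that is varied over a range.

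SAP 3.3 arrives at 165 per arm "allowing for approximately 15% loss to follow up".

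Protocol 9.3 is worded differently. Complete-case results are always reported but are described as biased. Next to them, "we will also report multiple-imputation based analysis for missing outcomes", or, as an equivalent, "likelihood methods which integrate over the missing outcome data based on the same assumption of missingness at random". It then adds: "Finally, we conduct sensitivity analyses in which the data are not assumed missing at random". The stated aim is to find how far the missing values would have to depart from expectation before the trial's conclusion changed. No threshold is attached to any of this. The one threshold in the section, more than 10%, concerns missing baseline covariates.

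Protocol 9.4.1 refers to the SAPs for further detail. The SAP revision history records no change to the handling of missing data.

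**The concern.** The two documents give different answers to whether the MAR and MNAR analyses will be reported when loss is at or below 15%. The protocol says yes. The SAP, which the analyst will work from, does not require them.

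The cut-off lies at about the loss the trial plans for, so the requirement may hinge on one or two participants. A rule of thumb that more than 20% missing is worrying does not show that less than 15% is safe. That depends on the size of the observed effect, the split of losses between arms, and how missing eyes differ from observed ones. A total percentage measures none of these.

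At stake is the question Protocol 9.3 itself asks: how extreme must the missing outcomes be to overturn the result? Below the trigger, nothing the SAP requires answers it. Loss is reported by arm (SAP 3.5 and 5.4), but counts do not show its effect on the estimate. If the choice to run these analyses is made after unmasking, they are no longer prespecified.

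Two smaller gaps go with this. SAP 6.3 names one shift parameter without saying whether it may differ by arm. Neither document says whether IPW/TMLE replaces the protocol's multiple imputation or likelihood method for REAGIR or is reported beside it.

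**Working it through.** **Inputs.** From SAP 3.3: SD 0.293, baseline correlation 0.216, 165 per arm (330 total), about 15% loss, two-sided alpha 0.05. From SAP 6.3: trigger at more than 15% missing. The gaps between missing and observed eyes, the arm splits and the design effect used below are assumptions; they are not in the documents.

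**1. The plan's own figure.** Residual SD = 0.293 × √(1 − 0.216²) = 0.286. Evaluable per arm = 165 × 0.85 ≈ 140. SE = 0.286 × √(2/140) = 0.0342. Detectable difference at 90% power = (1.960 + 1.282) × 0.0342 = 0.111; at 80% power, (1.960 + 0.842) × 0.0342 = 0.096. These round to the stated 0.11 and 0.10 logMAR, so the 15% loss is built into N = 330.

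**2. The trigger.** 0.15 × 330 = 49.5. With 49 missing (14.8%) neither analysis is required; with 50 both are. The chance of triggering is P(X ≥ 50), X ~ Binomial(330, true loss). The last column is a beta-binomial with an assumed design effect of 2.

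| True loss | Independent losses | Design effect 2 |
|---|---|---|
| 10% | 0.002 | – |
| 12% | 0.050 | 0.121 |
| 14% | 0.296 | – |
| 15% | 0.493 | 0.485 |
| 16% | 0.685 | – |
| 18% | 0.924 | 0.842 |
| 20% | 0.990 | – |

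Under the Protocol 9.3 wording the probability is 1 throughout.

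**3. What 49 missing outcomes could do.** Take 24 missing on RB-PDT and 25 on sham, leaving 141 and 140 observed. SE = 0.286 × √(1/141 + 1/140) = 0.0341, and the smallest significant difference is 0.0672. Let d be the observed benefit, and D1 and D0 the amounts in logMAR by which missing eyes are worse than observed ones on RB-PDT and sham. The benefit in all randomized eyes is

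d − (24/165) × D1 + (25/165) × D0.

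Holding the SE fixed and setting D0 = 0, significance is lost at D1 = (d − 0.0672)/(24/165):

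| Observed benefit d | p with no gap | Tipping D1, D0 = 0 | Tipping D1, D0 = 0.1 |
|---|---|---|---|
| 0.11 | 0.0014 | 0.294 (1.0 SD) | 0.399 |
| 0.10 | 0.0037 | 0.226 | 0.330 |
| 0.09 | 0.0088 | 0.157 (0.5 SD) | – |
| 0.08 | 0.0198 | 0.088 (0.3 SD) | 0.192 |

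With a 30/19 split the D0 = 0 values are 0.235 for d = 0.11 and 0.070 for d = 0.08.

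Shift-adjusted multiple imputation with Rubin's rules agrees. The p-value crosses 0.05 between D1 = 0.28 and 0.29 for d = 0.11, at about 0.22 for 0.10, between 0.15 and 0.16 for 0.09, and between 0.08 and 0.09 for 0.08.

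**4. Why the shift must be allowed to differ by arm.** A common shift of 0.5 logMAR moves the benefit by only (25 − 24)/165 × 0.5 = 0.003. By imputation, p is then 0.005 for d = 0.11 and 0.035 for d = 0.08. Both stay significant, so a common shift of that size says little about fragility.

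**The case against.** The best reply is that this is a clash of wording and not a missing analysis. Protocol 9.3 applies at any level of loss, and the SAP does not forbid the analyses below 15%. Only the first sentence of SAP 6.3 carries the condition; the sentences on MAR and MNAR carry none of their own. A team that followed both documents would do the work. This is fair as far as it goes. But the later sentences describe the very analyses that the first one makes conditional, so the conditional reading is the natural one, and the SAP should not leave it open.

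The SAP also plans several things with no threshold (6.2). The mixed model uses partial records under MAR. Eyes with perforation or TPK enter the primary analysis with their actual 6-month acuity, with LOCF as a sensitivity analysis. Another sensitivity analysis adds out-of-window outcomes. With consent, Protocol 7.2 allows follow-up data to be collected after withdrawal. These narrow the gap, but none is an MNAR or tipping-point analysis.

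The illustration uses the largest untriggered loss. With 16 missing per arm the tipping gap rises to about 0.46 for an observed 0.11 and 0.15 for 0.08. The fragile case, 0.08, is below the 0.10 detectable at 80% power. Both points are right and limit the size of the concern. The exact count of 50 also assumes 330 randomized, and SAP 6.3 does not say whether a value outside the 5–9 month window counts as missing; if it does, the trigger is reached at a lower true loss.

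Finally, a range of MNAR scenarios does not exclude shifts by arm, and the protocol could instead be aligned to the SAP. The first calls for a clarification. The second would remove the contradiction only by dropping a protocol commitment.

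**Conclusion.** The concern holds. SAP 6.3 makes conditional what Protocol 9.3 commits to at any level of loss. The cut-off is about the planned loss, and neither document reconciles the two. If loss runs at the planned 15%, whether the SAP requires its MAR and MNAR analyses is close to an even chance (49%); at 12% it is 5% under independent losses, or 12% with the assumed overdispersion.

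The consequence is moderate. At the design effect of 0.11 the result would survive a one-arm gap of nearly 1 SD. At an observed 0.08, less than one line of difference in the missing RB-PDT eyes removes significance. These figures rest on residual SD 0.286, 49 missing split 24/25, and assumed gaps. This should be corrected, but it does not affect the primary estimate, the alpha or the sample size.

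**What to change.** In SAP 6.3, delete the 15% condition and state that the MAR and MNAR analyses of the primary outcome are always reported. Let the shift differ between arms, and report the tipping point that Protocol 9.3 already asks for. State whether IPW/TMLE replaces or accompanies the protocol's multiple imputation or likelihood method for REAGIR.

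The cost is two or three sentences in the SAP and little extra code, since the methods are already specified. If IPW/TMLE is to replace the protocol's method, Protocol 9.3 also needs a short note limited to REAGIR.

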### 7.2 PARTICIPANT DISCONTINUATION/WITHDRAWAL FROM THE STUDY

Participants are free to withdraw from participation in the study at any time upon request. The reason for participant discontinuation or withdrawal from the study will be recorded on a dropout form, and the patient will be presented with an Informed Consent Form Addendum. With the patient's consent, we will monitor their surgical outcomes through collection of follow-up data from their medical provider and medical record.

Patients who sign the informed consent form and are randomized but do not receive the study intervention may not be replaced and will be included in the intent to treat analysis. Patients who sign the informed consent form, and are randomized and receive the study intervention, and subsequently withdraw, or are withdrawn or discontinued from the study, will not be replaced and will be included in the primary analysis.

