6.2. Analysis methods

Primary Outcome

Visual Acuity at 6 months. We will use a multiple linear regression model to estimate the mean difference between groups in BSCVA measured in logMAR at 6 months. The model will include covariates for treatment arm (a binary indicator variable for RB-PDT), indicators for study site (randomization strata), and baseline pinhole visual acuity. We propose a two-sided alpha of 0.05 for the primary analysis.

For study participants who experience perforation or the need for TPK this will be noted and BSCVA will be recorded prior to performing surgery (either corneal glue or TPK). These study participants actual 6-month visual acuity will be used in the primary analysis. As a sensitivity analysis, the last observation (at 3 weeks or 3 months) will be carried forward (LOCF) as the 6-month BSCVA.

The measurement window for the 6-month primary BSCVA outcome will be 5-9 months. The window was chosen after examining the distribution of measurement timing in masked data. As a sensitivity analysis, we will include all participants, including those who had their primary outcome measured out-of-window.

A supplementary analysis using linear mixed effects regression will be conducted to analyze all BSCVA data (including 3-week and 3-month observations). The model will include baseline BSCVA and treatment assignment as covariates (fixed effects) plus a random effect for patient to allow for repeated measures over time. Such analyses will be sharply distinguished from the primary pre-specified analysis. Permutation testing will be the basis of inference. Specifically, we will conduct 10,000 random permutations of treatment assignment, and conduct the primary regression analysis on these re-randomized data sets. We will then compare the observed regression coefficients to the randomization distribution, reporting the quantiles.

In all analyses, model adequacy will be checked by examination of residuals or other goodness of fit tests as needed. Inadequate model fit will prompt us to report alternative models. If there are chance imbalances in prognostic baseline patient characteristics, a secondary analysis will include them as covariates in the regression model.

Secondary Outcomes

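### REAGIR's missing-outcome models in SAP 6.3 use enrollment variables only; adding the 3-week and 3-month BSCVA and perforation/TPK already collected is a cheap improvement.

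*SAP*

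**What the plan says.** SAP 6.3 takes outcomes in the primary analysis to be "missing completely at random. We will relax this assumption slightly". If more than 15% of outcomes are missing, it adds two sensitivity analyses.

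- **Missing at random.** An inverse-probability-weighted estimator: "We will model the probability of censoring as a function of baseline patient characteristics with a logistic regression model". It is fitted "using a doubly-robust targeted maximum likelihood estimator that also includes an outcome model using the same covariates". The list reads: "Baseline characteristics used in the censoring model will include treatment arm, site, age, sex, occupation, medication use at enrollment, eye trauma, ocular measures at enrollment", the last item covering infiltrate or scar size, depth, epithelial defect, symptom duration and BSCVA.
- **Missing not at random.** A pattern-mixture model in which "we model BSCVA with a linear model as a function of covariates listed for the IPW estimator", with imputation by "adding a shift parameter, Δ , that we vary across a range of values". The range of values is not given.

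Three other places bear on the point.

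- SAP 6.2 plans a supplementary mixed model to "analyze all BSCVA data (including 3-week and 3-month observations"), with baseline BSCVA, treatment and a patient random effect.
- Protocol 9.3 plans multiple imputation or a likelihood analysis for missing outcomes and suggests the R package mice. It names no predictors for those outcomes.
- Protocol 7.2 says that treated participants who later withdraw "will not be replaced and will be included in the primary analysis".

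BSCVA and infiltrate/scar size are collected at 3 weeks and 3 months (SAP 6.1). Perforation or need for TPK is noted, with BSCVA recorded before surgery (SAP 6.2).

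**The concern.** A participant seen at 3 weeks and 3 months who then leaves enters all three SAP 6.3 models as if last seen at enrollment. How the eye has done since treatment is a plausible reason for leaving. If it is the reason, outcomes are not missing at random given enrollment variables alone, and weighting or standardising on those variables need not remove the bias.

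The stake is the credibility of the sensitivity analysis. It could agree closely with the complete-case result because both leave out the same information. The shift would be added to predictions that ignore known poor (or good) vision at month 3.

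Perforation makes this more pointed. SAP 6.2 now uses actual 6-month acuity for perforation/TPK participants in the primary analysis. One who perforates and is then lost has no primary value, and the SAP 6.3 models do not know about the perforation.

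**Working it through.** **The plan's own figure.** SAP 3.3 gives SD 0.293 and baseline correlation 0.216. Residual SD = 0.293 × √(1 − 0.216²) = 0.286, as stated. With 165 × 0.85 ≈ 140 evaluable per arm, SE = 0.286 × √(2/140) = 0.0342. The detectable difference from the t-test is 0.111 at 90% power and 0.096 at 80%, which round to the stated 0.11 and 0.10. The point disputes no design figure.

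**Assumptions the documents do not supply.** Dropout occurs after month 3. Its log-odds change by 1 per SD of 3-month BSCVA. The correlation of 3-month with 6-month BSCVA is varied.

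**Closed-form check, one arm.** For normal 3-month BSCVA and logistic dropout with slope 1, the mean among those remaining shifts by E[p(1 − p)]/(1 − p̄) SDs.

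- At p̄ = 0.15, numerical integration gives E[p(1 − p)] = 0.1127, so the shift is 0.1127/0.85 = 0.1326 SD.
- The 6-month shift is correlation × 0.286 × 0.1326: 0.6 × 0.286 × 0.1326 = 0.023 and 0.9 × 0.286 × 0.1326 = 0.034 logMAR.
- If dropout depends on early vision in one arm only, this is the bias in the contrast. In opposite directions it doubles, to 0.046 and 0.068. If alike in both arms, the shifts cancel under no treatment effect.

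**Simulation of the weighting.** One million participants per scenario, true effect −0.10, 3- to 6-month correlation given baseline 0.3 to 0.9. Absolute bias of weighting on arm and baseline BSCVA, in logMAR:

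| Early vision drives dropout | 15% missing | 20% missing |
|---|---|---|
| alike in both arms | 0.002–0.008 | 0.003–0.010 |
| in one arm only | 0.012–0.035 | 0.014–0.043 |
| in opposite directions | 0.022–0.068 | 0.029–0.087 |

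At 15% missing the baseline-weighted and complete-case estimates differ by no more than 0.0002. Adding 3-month BSCVA to the censoring model brings the bias to about 0.0015 or less in every scenario.

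**Trial-sized simulation.** 165 per arm, no true effect, 1,500 trials per scenario, 15% loss, correlations 0.6/0.8/0.9. With only sham dropout tied to poor vision the bias is 0.022/0.030/0.034; in opposite directions it is 0.044/0.059/0.065. Imputation by arm using baseline and 3-month BSCVA leaves 0.0013 or less.

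**Scale.** A one-arm bias of 0.02 to 0.03 is 0.02/0.11 = 18% to 0.03/0.10 = 30% of the design effect, or 0.6 to 0.9 of the SE above. Its sign depends on the arm: losing poor-seeing RB-PDT participants overstates benefit, and losing poor-seeing sham participants understates it.

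**The case against.** A reader might infer that withdrawn participants can return only through SAP 6.3, so that their early data are lost to the plan. The documents do not support that. The SAP 6.2 mixed model runs at any level of missingness and uses their 3-week and 3-month BSCVA. Protocol 9.3 plans imputation or likelihood analysis, and its limit to baseline variables applies to missing covariates, not outcomes. SAP 6.2 also carries early BSCVA forward for perforation/TPK cases as a sensitivity analysis. In large samples under the same dropout patterns (no true effect, exchangeable follow-up correlation, visit intercepts), the mixed model's bias was 0.002 or less.

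That answer is partial. The mixed model is supplementary, is not designated as a missing-data analysis and omits perforation/TPK. It states no treatment-by-time term, so with an effect that changes over time it would average across visits instead of estimating the 6-month contrast.

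A reader might also infer that SAP 6.3 must falsely confirm the primary result. That too goes beyond the text, for four reasons.

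- The shift can bracket such dropout if its range is wide enough.
- Patients and treating physicians are masked, and nothing in the documents indicates arm-specific dropout. Alike in both arms, the bias is close to zero.
- Halving the assumed slope, at correlation 0.8 and 15% loss, roughly halves the bias, to 0.018 and 0.032.
- The 0.216 correlation comes from bacterial ulcers between 20/60 and 20/400. REAGIR's population differs, and the SAP 6.3 models include further enrollment covariates that the simulation did not.

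**Conclusion.** The point holds as an improvement to SAP 6.3, not as a defect that invalidates the analysis. All three models condition on arm, site and enrollment variables only, while more informative data are already collected.

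Under the stated dropout assumptions, with 15% loss and correlation 0.6 to 0.9, the residual bias is about 0 to 0.008 logMAR if early response acts alike in both arms, 0.02 to 0.03 if in one arm only, and 0.04 to 0.07 in the opposite-direction extreme. The design effect is 0.10 to 0.11. Dropout pattern, slope and visit correlation are all assumed, and the documents do not say which pattern to expect. Since SAP 6.3 is triggered only above 15% missing, the 20% column shows what could apply when it runs.

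Separately, Protocol 7.2 and the SAP disagree. A regression on observed 6-month BSCVA does not include withdrawn participants who lack that value.

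**What to change.** In SAP 6.3, make the missing-at-random analysis a multiple imputation by arm, using mice as Protocol 9.3 already suggests. Predictors: the listed baseline covariates, 3-week and 3-month BSCVA, and perforation/TPK before last contact. Apply the shift to those imputations and state its range. A longitudinal version of the targeted estimator is not needed.

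Alternatively, designate the SAP 6.2 mixed model as a missing-at-random sensitivity analysis, add visit and treatment-by-visit terms, and report the 6-month contrast.

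Also reconcile Protocol 7.2 with the SAP's primary regression by saying which analyses include withdrawn participants.

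Cost: modest extra programming and no new data. At 15% loss there are about 165 × 0.15 ≈ 25 dropouts per arm, so the predictor set must be parsimonious. The change helps little for participants lost before week 3.

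### SAP 6.3 weights by the inverse of a modelled censoring probability; read literally this contradicts the stated aim, and it should be the inverse of the probability of being observed

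*SAP*

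**What the plan says.** SAP 6.3 leaves the primary analysis unweighted, on the assumption that outcomes are missing completely at random. It adds conditional checks: "If outcome data are missing for >15% of participants we will report results from sensitivity analyses for missing data". The first check relaxes the assumption, "assuming that outcomes are missing at random (MAR) with an inverse-probability weighted (IPW) estimator".

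One sentence then fixes the procedure:

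- **Model:** "We will model the probability of censoring as a function of baseline patient characteristics", by logistic regression.
- **Weight and its purpose:** the analysts "will use the inverse of the predicted probabilities from the model to re-weight the analysis population to reflect the full study population" as it stood at enrolment.
- **Estimator:** "using a doubly-robust targeted maximum likelihood estimator that also includes an outcome model using the same covariates".

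The covariates follow: "Baseline characteristics used in the censoring model will include treatment arm, site, age, sex, occupation, medication use at enrollment", then eye trauma and ocular measures including BSCVA. No interactions are listed. Nowhere does the SAP say that the probability to be inverted is that of being observed, or one minus the fitted value.

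**The concern.** The only probability the model is said to predict is that of censoring. Inverting it gives the largest weights to observed participants who were least likely to be lost, and the smallest to those who most resemble the lost. Weighting for missing outcomes must do the opposite. The rule and its stated purpose therefore disagree within one sentence, and a programmer who follows the rule gets the direction wrong.

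At stake is the missing-at-random check that SAP 6.3 names. It would be read when loss is above plan, to judge whether the unweighted primary result can be trusted. A reversed weight could make a sound result look fragile or a fragile one look supported.

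**Working it through.** **Figures in the plan.** SAP 6.3 gives none for the weights. SAP 3.3 supplies related inputs: about 15% loss, SD 0.293 and baseline-outcome correlation 0.216. These give a residual SD of 0.293 × √(1 − 0.216²) = 0.286, as stated, and a slope of 0.216 × 0.293 = 0.063 logMAR per SD of baseline acuity. Everything else below is an assumption.

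**Direction of the weight.** Let p = P(censored).

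| p | 0.05 | 0.10 | 0.20 | 0.40 |
|---|---|---|---|---|
| 1/(1 − p) | 1.05 | 1.11 | 1.25 | 1.67 |
| 1/p | 20 | 10 | 5 | 2.5 |

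The order reverses.

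**Exact two-stratum example.** Assume half the patients have severe ulcers, mean BSCVA is 0.2 (mild) and 0.6 (severe) logMAR, and p is 0.05 and 0.25, so 15% are lost overall. The true mean is 0.5 × 0.2 + 0.5 × 0.6 = 0.400.

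- Completers: severe share 0.375/(0.475 + 0.375) = 44.1%; mean 0.320/0.850 = 0.376.
- Weight 1/(1 − p): severe share 50.0%; mean 0.400.
- Weight 1/p: relative totals 0.475 × 20 = 9.5 and 0.375 × 4 = 1.5; severe share 1.5/11 = 13.6%; mean (9.5 × 0.2 + 1.5 × 0.6)/11 = 0.255.

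The error in the mean grows from −0.024 to −0.145.

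**Treatment contrast.** Simulation of 200,000 patients with about 15% censored, dropout log-odds 0.8 per SD of one baseline covariate, slope 0.063, residual SD 0.286 and true effect −0.11. Entries are bias in logMAR. The TMLE-type estimator includes the arm-by-covariate term, so its outcome model is correct.

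| Case | Estimator | Unweighted | 1/(1 − p) | 1/p |
|---|---|---|---|---|
| 1. Dropout slope opposite in the two arms | Raw difference | −0.0150 | −0.0011 | −0.1049 |
| | Baseline-adjusted regression | −0.0005 | −0.0007 | +0.0003 |
| | TMLE-type | −0.0005 | −0.0007 | −0.0012 |
| 2. Effect varies by 0.08 per SD | Raw difference | −0.0107 | −0.0020 | −0.0658 |
| | Baseline-adjusted regression | −0.0104 | −0.0017 | −0.0649 |
| | TMLE-type | −0.0016 | −0.0016 | −0.0015 |
| 3. Neither | Raw difference | +0.0014 | +0.0014 | +0.0019 |
| | Baseline-adjusted regression | +0.0011 | +0.0011 | +0.0010 |
| | TMLE-type | +0.0010 | +0.0011 | +0.0009 |

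The simulation standard error is about 0.0014. Adding a quadratic term that the outcome model omits moved TMLE in case 2 only to −0.0044 with 1/p, against −0.0023 with 1/(1 − p).

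**Why TMLE behaves this way.** The targeting step shifts the outcome model by a weighted mean of its residuals. If the outcome model is correct, that mean is zero in expectation under any weights. If it is wrong, weights of 1/(1 − p) still remove the error and weights of 1/p do not. Double robustness is lost.

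**A less favourable outcome model.** Assume 330 patients, 20% missing, true effect −0.10, covariate slope 0.12, dropout log-odds 1.0 per SD, effect modification 0.05 per SD, and an outcome model with main effects only.

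- Complete case −0.109; 1/(1 − p) weights −0.100.
- 1/p weights: plain weighting −0.147; TMLE −0.148 with a weighted fluctuation, or −0.126 with the weight as a clever covariate.
- With the interaction in the outcome model, TMLE under 1/p returns to −0.100.
- Milder inputs (slope 0.063, log-odds 0.5, effect modification 0.01 to 0.02): main-effects TMLE under 1/p gives −0.105 to −0.111.

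**The case against.** **The sentence states its own target.** Only 1/P(observed) makes the analysed patients represent those enrolled, and one logistic fit yields both probabilities. A statistician would probably read this as loose shorthand for inverse-probability-of-censoring weighting. That stands as evidence of intent, and it is why the point is minor. It does not make the rule correct, since no text tells the programmer to take the complement or how to code the missingness indicator.

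**The planned analysis need not enlarge the bias.** A reader might infer that the missing-at-random analysis, as specified, inflates the bias it is meant to remove. The documents do not support that. The estimator is a doubly robust TMLE, and the contrast also needs arm-dependent dropout or a varying effect before any bias arises. With severity-related dropout in the sham arm only and a true effect of −0.10, plain weighting by 1/p gave +0.014, as if the benefit had vanished. That estimator is not the planned one; TMLE stayed at −0.100.

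**The large TMLE error depends on chosen inputs.** It needs reversed weights, effect modification of half the treatment effect, and an outcome model without that interaction. The slope of 0.12 is also about twice the 0.063 that SAP 3.3 implies for baseline acuity. This stands as to size. The mechanism remains possible: the covariate list in SAP 6.3 names no interactions, while SAP 6.2 pre-specifies treatment interactions with organism and with prior antimicrobial therapy.

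**Other analyses address missing at random.** A reader might take this for the only such analysis. It is not. The mixed model on all BSCVA data in SAP 6.2 is likelihood-based, and Protocol 9.3 commits to multiple imputation of missing outcomes. Neither has the 15% trigger.

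**Conclusion.** Wrong as written; minor. The literal weight runs in the wrong direction and contradicts the sentence's stated aim, although 1/P(observed) was very likely meant.

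Followed literally, it could enlarge the bias of a plain weighted estimator when dropout differs by arm or the effect varies with covariates. It would also strip the planned TMLE of its double robustness. The TMLE would remain essentially unbiased with a correct outcome model. With an omitted interaction, the error on a true effect of −0.10 logMAR ranged from −0.005 to −0.011 under mild assumptions to −0.048 under strong ones. These sizes rest on assumed dropout models and effect variation; the documents give only the expected loss, the SD and the correlation.

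The primary estimate, test and interval are untouched. Planned loss is about 15% and the trigger is more than 15%, so the analysis may never be run.

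**What to change.** Reword SAP 6.3 to say that the logistic model gives the probability that the 6-month BSCVA is observed, and that observed participants are weighted by the inverse of that probability, equivalently 1/(1 − P(censored)). State that the missingness indicator passed to the TMLE routine is coded 1 = observed.

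This is one or two sentences, with no data or operational cost, and is best made before unmasking.
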